Missing post-intervention data is a risk for this trial as some of the secondary outcomes are collected via primary data collection (an online survey) and the attrition is likely to be high given that the follow-up period is over a relatively long period of time (4 months - 12 months later) and the professionals may have left their employer.

Covariates

- If the covariate has more than 30% of the data missing, we will drop the covariate.
- For each covariate in the main model (see the “Covariates” section) that has up to 30% of the data missing, we will regress an indicator of missingness on the other covariates in the main model and outcomes using logistic regression, clustering the standard errors at the team level. If any of the coefficients on the covariates of the missingness model are statistically significant at the 5% level, then data is not missing completely at random (MCAR).
- To distinguish between whether the data is missing at random (MAR) i.e. missing conditional on observables or missing not at random (MNAR) i.e. missing conditional on unobserved variables, for all the covariates that were not MCAR we then impute the missing values of the covariate of interest (using a missing category for categorical variables and multiple imputation for numeric variables) and compare the treatment estimates using the imputed data and data restricted to the complete cases. If the results are similar (i.e. significant / insignificant, the same direction and only differing in magnitude of up to 20%), then data is likely to be missing at random (MAR). If the results are dissimilar, the data is likely to be missing not at random (MNAR).

If the data on covariates are MCAR or MAR, then complete case analysis is likely to be unbiased but less well powered. To maintain power we use a missing category for categorical variables as missingness is likely to be a predictor in itself and multiply impute missing numerical covariates (including pre outcome measures). We ignore the clustered structure of the data because cluster sizes are small, cluster follow-up rates may be highly variable and we expect the ICC to be low (we assume the ICC to be 0.03 in power calculations)²¹.

Outcomes

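### The rule that labels incomplete covariates MAR or MNAR by comparing imputed and complete-case treatment effects cannot make that distinction and is often tripped by chance when the effect is small

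*Protocol*

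**What the plan says.** The covariate part of the Missing data strategy runs in four steps.

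1. Dropping: "If the covariate has more than 30% of the data missing, we will drop the covariate".
2. MCAR screen: for each remaining incomplete covariate, a missingness indicator is regressed on the other covariates and the outcomes. "If any of the coefficients on the covariates of the missingness model are statistically significant at the 5% level", MCAR is rejected.
3. MAR or MNAR: "for all the covariates that were not MCAR we then impute the missing values of the covariate of interest". Here categorical variables receive an extra level for missing values, and numeric ones are multiply imputed. The treatment estimate is then compared with the complete-case estimate. Agreement means "significant / insignificant, the same direction and only differing in magnitude of up to 20"%, and leads to the label MAR. Otherwise: "If the results are dissimilar, the data is likely to be missing not at random (MNAR".
4. Handling: for covariates labelled MCAR or MAR, the plan keeps the extra level for categorical variables and will "multiply impute missing numerical covariates (including pre outcome measures"). No handling is stated for a covariate labelled MNAR.

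**The concern.** Whether data are MAR or MNAR depends on values that were not observed. Comparing two analyses of the observed data cannot settle it, whatever tolerance is chosen.

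The statistic chosen is also a poor one. It is the treatment effect, which randomisation makes largely insensitive to how a baseline covariate came to be missing. The tolerance is relative to that effect, so it shrinks towards nothing as the effect approaches zero. A small effect is realistic here: the Outcome measures section itself describes the administrative outcome, now primary, as hard to shift with a light-touch programme.

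Two things are at stake. A chance MNAR label could lead readers to distrust a sound result. And because handling is given only for the other two labels, the analyst would have to choose it for the affected covariate with both versions of the treatment effect in view.

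**Working it through.** **Logic.** Two cases show that the rule can point the wrong way.

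- Missingness of the covariate depends on the outcome, a dependence that the plan's own screen looks for. The data are MAR, yet complete-case and imputed estimates can differ. The rule then says MNAR.
- Missingness depends only on the covariate's own unseen value. The data are MNAR, yet the two treatment estimates can agree. The rule then says MAR.

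For categorical covariates the imputation is a missing category, which does not test a MAR assumption at all.

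**Inputs from the Protocol.** 60 teams, half treated; 150 children per team; teams of 6-8 social workers (7 used, before non-response); individual-level R2 0.8; team-level R2 0.1; two-sided 5% (Sample size / MDES calculations; Design table). For the ICC, "we assume the ICC to be 0.03 in power calculations". The Protocol gives no expected missing fraction, so 5-30% is an assumed range, with 30% the plan's own ceiling. It also does not say which estimate is the base for the 20%; the simulations tried both and the rates hardly changed.

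**The plan's own figure.** The standard error is sqrt[0.03 x 0.9/(0.25 x 60) + 0.97 x 0.2/(0.25 x 60 x 150)] = sqrt(0.001800 + 0.0000862) = 0.0434. With 4 x (15 - 2) - 3 = 49 degrees of freedom the multiplier is 2.859, so the MDES is 0.124 against the stated 0.127. Power at 0.127 is 81.8% against 80%. The inputs reproduce the plan well enough to use.

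**Chance of exceeding 20% under a null effect.** Let v_team = 0.03 x 0.9 = 0.027, let v_ind = 0.97 x 0.2 = 0.194, let n be the number per team and m the missing fraction. If imputation recovers the full-sample precision, the complete-case estimate is the imputed one plus independent noise. The ratio of that noise to the estimate is Cauchy with scale

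s = sqrt{ (v_ind/n) x [m/(1 - m)] / (v_team + v_ind/n) },

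and P(differ by more than 20%) = 1 - (2/pi) x atan(0.2/s).

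At n = 150 and m = 0.3: v_ind/n = 0.00129, s = 0.140, P = 39%. At n = 7 and m = 0.3: v_ind/n = 0.0277, s = 0.466, P = 74%.

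**Full rule by simulation.** Sign, significance and the 20% criterion were applied together, with team-clustered OLS, multiple imputation, no treatment effect and truly MAR data. Simulation error is up to about 3 points per cell.

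| Missing | 150 per team: formula | 150 per team: simulated | 7 per team: formula | 7 per team: simulated |
|---|---|---|---|---|
| 5% | 15% | 12-20% | 44% | 29-45% |
| 10% | 22% | 18-23% | 55% | 39-58% |
| 20% | 31% | 22-31% | 67% | 54-72% |
| 30% | 39% | 35-40% | 74% | 58-76% |

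If missingness depends on the outcome, the 30% cells at 7 per team become 63-79%; one such cell at 150 per team gave 42%.

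**Discrimination.** At 30% missing, truly MNAR data are flagged in 33-45% of trials (150 per team) and 63-76% (7 per team). True MAR gives 35-40% and 58-76%. The label carries almost no information.

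**Dependence on R2.** The 0.8 is justified in the Protocol for the SDQ score, and no R2 is given for the escalation outcome. With R2 = 0.3 (assumed), v_ind = 0.97 x 0.7 = 0.679. At 150 per team the formula then gives 36%, 48% and 57% at 10%, 20% and 30% missing.

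**With a real effect.** At an effect of 0.127 with MAR data the rule says MNAR in about 1-12% (150 per team) or 13-47% (7 per team). At 0.3 with 7 per team it does so in 0-6%.

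**The screen before the rule.** With k independent tests at 5%, a true MCAR is rejected with probability 1 - 0.95^k: 40%, 54% and 64% for k = 10, 15 and 20. Both the count and the independence are assumptions.

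**The case against.** A reader might infer that between a third and three quarters of all null trials would be labelled MNAR even when values are missing completely at random. The documents do not support that. The comparison is reached only after the MCAR screen rejects, so every rate above is conditional on that step. With 150 children per team and the plan's own R2 of 0.8, rates of that size arise only near the 30% ceiling, and they drop sharply once there is a real effect.

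A reader might also infer that the label governs the handling of covariates in general. It does not. The Covariates section already gives a missing level to child gender, age group, ethnicity, disability, type of social care intervention, asylum-seeking status and social worker change, and to staff gender, role and contract type. The open choice concerns the few covariates without such a level, mainly numeric ones such as the prior outcome measure.

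It is fair to add that the Protocol words the label as likely rather than certain and attaches no action to it, that a SAP might supply one, and that MCAR and MAR lead to the same handling, so a false MCAR rejection does little harm by itself.

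These points limit the size of the problem. They do not make the inference valid. The rule is stated in the Protocol, so it is not a detail left for later, and the stated handling is still conditional on a label derived from the treatment effect.

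**Conclusion.** The concern holds as a minor-to-moderate methodological correction. The rule cannot distinguish MAR from MNAR, and the relative tolerance fails near a zero effect. Given a failed MCAR screen, a null effect and truly MAR data, it would say MNAR in roughly 12-40% of trials at 150 per team and 29-79% at 7 per team, for 5-30% missing. The ranges rest on the plan's ICC and R2 values and on an assumed missing fraction. A lower R2, or fewer respondents per team, raises them; a real effect lowers them. The main estimator is not invalidated. The practical harm is an uninformative label and an unfixed choice for a few covariates, made with the treatment effect visible.

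**What to change.** Delete the MCAR/MAR/MNAR classification for covariates. For every baseline (pre-randomisation) covariate with up to 30% missing, always use the method the section already names: a missing category if categorical, multiple imputation if numeric. Report the complete-case treatment estimate as a sensitivity analysis only, with no label drawn from the comparison.

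This does not deal with covariates measured after allocation: the T6 survey measure, change of social worker, and status changes during the intervention period. They are a separate issue.

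The cost is the loss of a diagnostic that tells the reader almost nothing. The edit removes two bullets and the condition on the handling paragraph, and reduces the analysis work.

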- For each outcome, we will regress an indicator of missingness on the covariates in the main model (see the “Covariates” section) using logistic regression with standard errors clustered at the team level. If any of the coefficients on the covariates of the missingness model are statistically significant at the 5% level, then data is not missing completely at random (MCAR).
- In particular, we are interested in the coefficient on the treatment dummy. If it is not significant, this suggests that the data is missing experimentally at random (MEAR) (where data may be correlated with observable or unobservable variables, but not with treatment assignment) and we will only include observations for which we have the outcome data controlling for any variables which are significant (if they are not already specified in the “Covariates” section above).
- In line with WWCS statistical guidance, if the data on outcomes is missing experimentally not at random (MENAR) e.g. due to large differential attrition, then we will multiply impute within the treatment condition.

Sensitivity analysis following multiple imputation

Given that there may be a substantial proportion of outcome data to impute, we check the sensitivity of our results to the imputation strategy. We will:

²¹ See Taljaard, M., Donner, A., & Klar, N. (2008). Imputation strategies for missing continuous outcomes in cluster randomized trials. *Biometrical journal. Biometrische Zeitschrift*, 50(3), 329–345. <https://doi.org/10.1002/bimj.200710423>

- impute using baseline observation carried forwards (BOCF)
- impute using control drifted observation carried forward (CDOCF). This is done by carrying forward the baseline observation and then adding the “drift” from the comparator group to take into account the amount their outcome would have changed in the absence of treatment. The drift is calculated using an autoregression model for the comparator group.

Reporting

In addition to handling missing data and conducting sensitivity analyses, we also report some summary statistics to allow for a qualitative assessment of the impact of missing data on the treatment effect estimate.

- For each outcome and covariate, we will report the percentage of missing data alongside summary statistics
- Rates of loss to “post” data collection for the arms of the trial

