Focus groups	T10-T12	
We will send information about the focus groups to the practitioners via the Kitbag super lead and then purposively sample aiming for a heterogenous sample of practitioners from different team types and of different roles.
 
For the focus group discussions for the super leads, all will be invited to attend.

Interviews (n=16)	T10-T12	
Children: Practitioners who attend the focus group discussion will be asked to identify children on their caseload who may be open to participating.
 
Foster carers: the Kitbag leads in the fostering teams will be asked to send information about the interviews to the foster carers. We

		will purposively sample aiming for a heterogenous sample of foster carers of children of different ages.
Survey (assume 10% response rate)	T1 T13	A survey will be shared with all staff (i.e. no sampling) across intervention and comparator teams: 
 • Social workers and family support workers (includes Kitbag Leads) • Inhouse foster carers (the survey will be adapted slightly for this group) • Team Managers
Observations of workshops (n=4)	T3-T4	A researcher or research assistant will observe at least one workshop per local authority.

Analysis

Qualitative data preparation and analysis of interview and observational data

Interviews will be recorded, transcribed and pseudonymised prior to analysis. Qualitative analysis of interview and observational data will use NVivo software and follow a thematic analysis approach. This will involve data familiarisation, checking accuracy of transcription, labelling the data with descriptive codes and developing themes which describe patterns across the data to answer the pre-specified research questions. Analysis will look for patterns, consistencies and inconsistencies across different informants and time points that might be informative for the research questions.

The following steps will be taken to ensure rigor in the analysis and reporting of qualitative data:

- Confidence that the findings are an accurate reflection of participant experience will be ensured through presentation of examples of participant responses using quotes, and triangulation between different informants and data collection methods.
- The degree to which findings are transferable to other contexts will be considered through detailed description of contextual factors, and collection of data from a range of informants to gather a range of perspectives.

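### A non-significant treatment coefficient in the outcome-missingness model is taken to show missingness unrelated to arm, so the three survey-based secondary outcomes can be reported from complete cases with no sensitivity re-estimate

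*Protocol*

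**What the plan says.** The rule is in the Protocol, Missing data strategy, Outcomes. An indicator of missingness for each outcome is regressed on the main-model covariates by logistic regression with standard errors clustered by team. Any covariate coefficient that is "statistically significant at the 5% level, then data is not missing completely at random (MCAR") rules out missing completely at random. The treatment coefficient is then singled out: "If it is not significant, this suggests that the data is missing experimentally at random (MEAR"). In that case "we will only include observations for which we have the outcome data controlling for any variables which are significant".

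The alternative branch reads: "if the data on outcomes is missing experimentally not at random (MENAR) e.g. due to large differential attrition, then we will multiply impute". That imputation is done separately by arm. No margin or size of differential attrition is given.

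The only sensitivity re-analyses of missing outcomes are baseline observation carried forward (BOCF) and control-drifted observation carried forward (CDOCF). They stand under the heading "Sensitivity analysis following multiple imputation", and their stated purpose is that "we check the sensitivity of our results to the imputation strategy".

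The same chapter expects high attrition on the survey outcomes. The Data collection schedule of the process evaluation has the row "Survey (assume 10% response rate").

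**The concern.** The rule draws a conclusion of no difference from failure to find one, with no equivalence margin, and that conclusion decides which analyses are run. On the non-significant branch nothing has been imputed, so a check on the imputation strategy has nothing to act on. The outcome is then estimated once, from responders only.

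This matters for the three outcomes collected by online survey: worker self-efficacy, worker stress and carer self-efficacy. They are the outcomes with the most expected non-response, and staff know whether their team received Kitbags, so willingness to answer may depend on arm. The test compares how many respond in each arm. It does not compare who responds, and a complete-case contrast can be biased by either.

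**Working it through.** The protocol gives no operating characteristics for the missingness test, so there is no figure to reproduce. I approximated the treatment coefficient test by a two-sample comparison of response proportions, with sample size deflated for clustering.

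**Inputs**
- Staff per arm, lower value: 300. Table 2 gives this as the intervention-group count. The control count is not given; equal size is assumed.
- Staff per arm, upper value: 500, half of the c.1000 social workers under Data protection, again assuming equal arms.
- Carers: 424 in the intervention group (Table 2), with an equal control group assumed.
- Teams: 30 per arm (sample size table).
- ICC: 0.03, the protocol's planning value. The ICC of missingness itself is not stated, so 0 to 0.10 is shown.
- Two-sided 5% test. Response is 10% in one arm (the schedule's assumption) and 15% in the other (assumed gap).

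**Formulas**
- Design effect = 1 + (m − 1) × ICC, where m = n per arm / 30; effective n = n / design effect.
- z = (|p1 − p0| − 1.96 × SE_pooled) / SE_unpooled; power = Φ(z); miss rate = 1 − power.

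**10% v 15% at ICC 0.03**
- 300 per arm: m = 10; design effect 1.27; effective n = 236.2. SE_pooled = √(2 × 0.125 × 0.875 / 236.2) = 0.0304; SE_unpooled = √((0.09 + 0.1275) / 236.2) = 0.0303. z = −0.318, so the miss rate is 0.625.
- 500 per arm: m = 16.7; design effect 1.47; effective n = 340.1. SE_pooled = 0.0254, SE_unpooled = 0.0253. z = 0.012, miss rate 0.495.
- 424 carers per arm: m = 14.1; design effect 1.394; effective n = 304.2. z = −0.096, miss rate 0.538.

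**Sensitivity to the inputs**

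| Setting | 300 per arm | 500 per arm |
|---|---|---|
| 10% v 15%, ICC 0 | 0.54 | 0.33 |
| 10% v 15%, ICC 0.03 | 0.62 | 0.50 |
| 10% v 15%, ICC 0.10 | 0.73 | 0.68 |
| 30% v 40%, ICC 0.03 | 0.37 | 0.22 |
| 50% v 60%, ICC 0.03 | 0.41 | 0.25 |
| 10% v 20%, ICC 0.03 | 0.14 | 0.04 |

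Entries are miss rates. A doubling of response is usually caught; one arm having 1.5 times the responders of the other often is not. With 300 per arm, the gap detectable with 80% power is about 9 points from a 10% base and 13 points from 50%.

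**Equal rates, different responders.** Suppose response is 10% in both arms, and in one arm only the odds of responding rise by a factor of 1.2 per SD of the outcome. Simulation gives a complete-case bias of about 0.16 SD (0.04 SD at 80% response). The factor 1.2 is purely illustrative. This shows that a correct finding of equal response rates is not a finding of no bias; it is not an estimate for this trial.

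**The case against.** The strongest replies are these.

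- **The plan has a check that does not pass through the gate.** Under Reporting, within the missing data strategy, routinely collected outcomes are modelled with an indicator of missing survey data and its interaction with treatment. Loss by arm and a baseline table by arm and response are also reported. This stands, and it means the plan does not ignore selection by arm. But the interaction is fitted to other outcomes, the protocol presents it as a proxy, and it re-estimates no survey outcome.
- **The imputation branch is loosely worded.** It mentions large differential attrition and does not repeat the p-value, so judgement might enter. That is fair as far as it goes. Yet the non-significant branch prescribes complete cases outright, and no other threshold is given.
- **The bias from a missed gap in rates is modest beside the sampling error.** With a correlation of 0.3 to 0.5 between outcome and response propensity (assumed), a missed 10% v 15% gap biases the contrast by (1.755 − 1.554) × 0.3 to 0.5 = 0.06 to 0.10 SD. With 30 v 45 responders the unadjusted 95% CI half-width is 1.96 × √(1/30 + 1/45) = 0.46 SD. This stands and limits the severity.
- **Complete-case analysis with covariates can be a sound primary analysis.** Agreed. The fault is that a weak test selects it and removes the checks.

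A reader might infer that the gate itself causes large bias, or that running imputation and carry-forward for everyone would cure it. The documents support neither. Large bias at equal response rates comes from assumed selection on the outcome. Imputation within arm assumes missing at random and would largely reproduce it. BOCF and CDOCF need a pre value, which for the surveys is now taken at T6, after launch, and which most staff would lack if response is near 10%.

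**Conclusion.** The concern holds for the three survey-based secondary outcomes. A non-significant coefficient is treated as showing that missingness is unrelated to arm, and the outcome can then be reported without any re-estimate under a different missing-data assumption. With 300 to 500 staff per arm, the test misses a 10% v 15% response gap about 49.5% to 62.5% of the time (33% to 73% over ICC 0 to 0.10).

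This rests on equal arm sizes, on the planning ICC applying to missingness, and on response near the schedule's 10%. That row still shows the first survey at T1, although the Survey section moves it to T6. The weakness is smaller but remains at 30% to 50% response. The carer figure also assumes that both arms are surveyed; the Survey section mentions intervention-group carers only, whereas the schedule covers both arms.

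The scope is limited. The administrative primary outcome is little affected, and imputation of numeric covariates and pre measures is governed by a separate rule.

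**What to change.** In Missing data strategy, Outcomes:

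1. Remove the significance test as the switch between analyses. Name the primary missing-data approach for each survey outcome in advance; covariate-adjusted complete-case analysis is acceptable.
2. Report the difference in response between arms with its 95% CI, and state that similar rates do not exclude different selection by arm.
3. Whatever the p-value, run multiple imputation within arm, plus a sensitivity analysis that allows arm-specific departures from missing at random, such as a delta-adjusted or tipping-point analysis over a stated range.
4. Keep BOCF and CDOCF only for respondents with a pre value, and note that this value is measured at T6, after launch. Retitle the sensitivity section so that it no longer depends on imputation having been used.
5. Keep the treatment-by-missingness interaction on routine outcomes as supporting information.

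The cost is a change of wording and a few extra model runs on data already held. Survey results would be shown with a range and may look less certain.
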